4.2 Intervention

Patient Population

Patients with histologically confirmed locally advanced or metastatic disease of the following tumor types who meet the eligibility criteria:

- (1) melanoma
- (2) bladder cancer

[figure not shown]
Sample Size

Up to 81 patients will be enrolled in two separate arms: one for melanoma and one for bladder cancer. It is estimated that approximately 85% of enrolled patients will be considered evaluable for both the clinical and research (WES, RNAseq) study endpoints, with an approximate 10% failure rate related to the biopsy, biopsy sample preparation and sequencing, and an approximate 5% failure rate for clinical reasons (i.e. patient replaced for clinical reasons and non-evaluable for response). Based upon these calculations, we estimate that we will have approximately 60 bladder patients and approximately 8 melanoma patients with both clinical and research (genomic) data for analysis, consistent with the protocol statistical plan.

[figure not shown]
Treatment Schema

All eligible patients with melanoma will receive ipilimumab at a dose of 3 mg/kg combined with nivolumab at a dose of 1 mg/kg. The ipilimumab and nivolumab will be dosed every 3 weeks for 4 doses. Thereafter, patients may be eligible to continue to receive nivolumab monotherapy at a dose of 240 mg administered every 2 weeks, or at a dose of 480mg administered every 4 weeks, for up to 2 years. If the patient is clinically benefitting, the PI and treating investigator may elect to continue treatment beyond 2 years..

Schema for Melanoma (prior to Amendment 11)

Schema for Melanoma (after Amendment 11)

[figure not shown]
All eligible patients with bladder cancer will receive nivolumab at a dose of 240 mg administered every 2 weeks, or at a dose of 480 mg administered every 4 weeks, for up to 2 years. If the patient is clinically benefitting, the PI and treating investigator may elect to continue treatment beyond 2 years.

Patients with bladder cancer who have confirmed disease progression after treatment with nivolumab monotherapy may be treated with the combination of nivolumab and ipilimumab provided all of the following conditions are met:

[figure not shown]

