5.0 THERAPEUTIC/DIAGNOSTIC AGENTS

PRODUCT INFORMATION TABLE: Please also see Pharmacy manual in Appendix 1.

Product Description and Dosage Form	Potency	Primary Packaging (Volume)/Label Type	Secondary Packaging (Qty) /Label Type	Appearance	Storage Conditions (per label)
Nivolumab BMS-936558-01 Solution for Injection	100 mg (10 mg/mL)	10 mL vial	5-10 vials per carton/ Open-label	Clear to opalescent colorless to pale yellow liquid. May contain particles	Protect from light and freezing
Ipilimumab Solution for Injection	200 mg (5 mg/mL)	40 mL vial	4 vials per carton/Open-label	Clear, colorless to pale yellow liquid. May contain particles	2 to 8°C. Protect from light and freezing.

*Nivolumab may be labeled as BMS-936558-01 Solution for Injection

If stored in a glass front refrigerator, vials should be stored in the carton. Recommended safety measures for preparation and handling of nivolumab and ipilimumab include laboratory coats and gloves.

For additional details on prepared drug storage and use time of nivolumab or ipilimumab under room temperature/light and refrigeration, please refer section 8.8 and to the BMS-936558 (nivolumab) and Ipilimumab Investigator Brochure section for "Recommended Storage and Use

Conditions"

Estimated Requirements for Study Drug:

Drug	Source	Required Quantity
--------------------	----------------------	---------------------------------

For melanoma cohort:

Nivolumab	BMS	Up to 667,200 mg Induction - 19,200 mg (60 pt x 80 kg x 1 mg/kg x 4 doses) Maintenance – 648,000 mg (60 pt x 80 kg x 3 mg/kg x 45 doses)
Ipilimumab	BMS	Up to 57,600 mg (60 pt x 80 kg x 3 mg/kg x 4 doses)

For bladder cohort:

Nivolumab	BMS	Up to 705,600 mg Induction – 57,600 mg (60 pt x 80 kg x 3 mg/kg x 4 doses) Maintenance/ Monotherapy – 648,000 mg (60 pt x 80 kg x 3 mg/kg x 45 doses)
Ipilimumab	BMS	Up to 19,200 mg (60 pt x 80 kg x 1 mg/kg x 4 doses)

Drug Dosing

For patients receiving nivolumab monotherapy, the drug shall be dosed at a dose of 240 mg (every 2 weeks) or 480 mg (every 4 weeks).

For patients initiated on treatment, or initiated on crossover treatment after the approval of Amendment 11, the dosing for the combination of ipilimumab and nivolumab will be ipilimumab 3 mg/kg and nivolumab 1 mg/kg for both bladder and melanoma patients. For patients who initiated treatment with the combination of ipilimumab and nivolumab prior to Amendment 11, they will maintain their current dosing/schedule.

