9.0 TREATMENT/INTERVENTION PLAN

Treatment of protocol eligible patients with nivolumab or nivolumab and ipilimumab will follow the treatment plan described in section 4.2. Treatment with nivolumab or nivolumab and ipilimumab are deemed experimental treatments. Treatment with nivolumab or nivolumab and ipilimumab will occur in the outpatient setting.

The following interventions on treatment are considered routine and will be performed according to the schedules in section 10.0 with indicated time windows.

- Disease assessment by RECIST 1.1 (CT scan CAP, or alternative imaging as needed for disease assessment and MRI or CT brain, if applicable)
- Medical History
- Vitals (including Height and Weight)
- Physical Exam
- Pregnancy test (serum or urine)- only if WOCBP
- Chemistry Panel Comprehensive Metabolic Panel (including AST, ALT, total bilirubin) LDH, TSH, Total or Free T3, Total or Free T4, albumin
 - Note: 1. Total T3 or Free T3 and Total T4 or Free T4 may be collected according to treating physician preference and institutional availability.
- Hematology Panel – CBC with differential
- HIV, Hepatitis B and Hepatitis C tests

The following interventions on treatment are considered research and will be performed according to the schedules in section 10.0 with indicated time windows. Additional details are available in Appendix 3.

- Tumor Biopsy
- Research Blood draw for collection of PBMCs and serum (6 time points for bladder crossover cohort and melanoma cohort, 8 time points for bladder monotherapy cohort)

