10.0 EVALUATION DURING TREATMENT/INTERVENTION

10.1 Standard Evaluation

Flowchart 1 - Nivolumab Monotherapy for Patients with Bladder Cancer

Study Section	Screening	Baseline	Initial Treatment							Treatment beyond Week 12 (up to 2 yrs) ^h (+/- 3 d)	End of Nivolumab Treatment ^e	
			0	2 (+/- 3 d)	4 (+/- 3 d)	6 (+/- 3 d)	8 (+/- 3 d)	10 (+/- 3 d)	12 (+/- 3 d)		If patient has not proceeded to Crossover Therapy	Last Day (EOT Only)
Study Week												
Study Day	-28 to -1	-14 to -1 (or as stated)	1	15	29	43	57	71	82			
Drug Administration												
Nivolumab (240 mg or 480 mg) ^a			X	X	X	X	X	X	x	q 2 wks (240 mg) OR q 4 wks (480 mg)		
Tumor Assessments												
Disease Staging	X											
Disease Assessment by RECIST 1.1 (including MRI or CT brain at screening)	X		Every 6 weeks (+/- 7 days) from first dose for the first 24 weeks and then every 12 weeks (+/- 7 days) thereafter until study discontinuation. ⁱ MRI or CT brain required at screening, but only necessary for subsequent disease assessments in patients with known disease metastatic to the CNS ^f									
Tumor Biopsy	X		2 weeks (- 5, +5 days) from first dose and before 2 nd dose of therapy ^g							At tumor progression (+ 14 days) ^g		
Other Examinations												
Eligibility Assessment and Informed Consent	X											
Demographics	X											
Medical History	X											
ECOG, Vital Signs (including Height, Weight), Physical Exam & collection of concomitant medications	X		X	X	X	X	X	X	X	q 2 weeks/ q 4 weeks ^j	X	X
EKG	X											
Adverse Events Assessment	X		X	X	X	X	X	X	X	q 2 weeks/4 weeks ^j	X	X
Labs & Assays												
Pregnancy Test (see Section 5.2.17, serum based) ^b		3mL									X	X
Urine pregnancy test (within 3 days prior to dosing) ^b			X	X	X	X	X	X	X	q 2 weeks/4 weeks ^j		
Chemistry (Comprehensive Metabolic Panel, LDH, TSH) ^c		X	X	X	X	X	X	X	X	q 2 weeks/4 weeks ^j	X	X
Blood Hematology (CBC with differential) ^c		X	X	X	X	X	X	X	X	q 2 weeks/4 weeks ^j	X	X
Research Blood Draw [mL] ^c	60mL		60mL	60mL	60mL	60mL	60mL	60mL	60mL		60 mL	
HIV, Hepatitis B and Hepatitis C	X											
Survival Follow-up ^d											X	X

- a. Nivolumab may be dosed no less than 11 days from the previous dose of drug.
- b. Pregnancy tests are not required if the patient is a male or a woman not of child-bearing potential
- c. Blood drawn prior to dosing drug. Blood must be drawn at all required timepoints. Results of thyroid functions tests are not required prior to dosing drug.

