- d. Patients will be followed up by telephone (or by office visit) every 12 weeks (+/- 2 weeks) for 4 years from the start of treatment or until death. Follow-up calls or visits should begin 12 weeks +/- 2 weeks from the last study contact.
- e. If the patient will not initiate treatment with the combination, end of treatment should be initiated as per Study Flowchart 3
- f. Patients who discontinue treatment due to toxicity will continue to follow the study procedures (without treatment) for 12 weeks from the start date. They will require all disease assessments according to study protocol, however, after 12 weeks, all other study assessments (PE, Laboratory assays) will be performed every 12 weeks (+/- 7 days). If patients discontinue treatment due to toxicity after they have been on treatment for 12 weeks, then the q 12 week follow up will begin after the patient's end of treatment. If the patient did not have an end of treatment visit, the q 12 week follow up will begin after the patient's last dose. Patients who experience progression of disease after discontinuing treatment early due to toxicity should move to survival follow-up. Patients in toxicity follow-up who initiate treatment with a new therapy will be immediately moved to survival follow-up.
- g. Optional
- h. Patients with a proven ability to tolerate treatment who have been on study for longer than one year will have visits with physicians every 4 weeks and treatment-only visits in between.
- i. Patients who have completed 26 weeks of treatment may elect to complete disease assessment scans every 6 months (24 weeks). This will continue until study discontinuation, under the treating investigator's discretion
- j. Frequency of ECOG, Vital Signs, Physical Exam, AE Assessments and all lab panels should follow the frequency of Nivolumab treatment (q 2 weeks or q 4 weeks) and should occur simultaneously within the same visit

Flowchart 2 - Nivolumab plus Ipilimumab Combination Treatment for Patients with Melanoma

Study Section	Screening	Baseline	Initial Treatment				Treatment beyond Week 12 (up to 2 yrs) ^{e,h} (+/- 3 d)	End of Treatment	
Study Week			0	3 (+/- 3 d)	6 (+/- 3 d)	9 (+/- 3 d)		Last day	Last day +6 weeks (+/- 1 wk)
Study Day	-28 to -1 (or as stated)	-14 to -1	1	22	43	64			
Drug Administration									
Nivolumab 1 mg/kg			X	X	X	X			
Nivolumab 240 mg or 480 mg ^a							q 2 wks (240 mg) OR q 4 wks (480 mg)		
Ipilimumab 3 mg/kg			X	X	X	X			
Tumor Assessments									

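### Flowchart 1 marks both nivolumab dose options at every 2-weekly visit through week 12, which conflicts with the 4-weekly interval that Sections 1, 4.2 and 5 give for 480 mg

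*Combined protocol and SAP*

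**What the plan says.** Section 4.2 gives bladder patients "nivolumab at a dose of 240 mg administered every 2 weeks, or at a dose of 480 mg administered every 4 weeks". Section 5.0, under Drug Dosing, repeats the pairing for monotherapy: "the drug shall be dosed at a dose of 240 mg (every 2 weeks) or 480 mg (every 4 weeks". Section 1.0 agrees, so the text of the protocol always attaches each dose to its own interval.

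Flowchart 1 in Section 10.1 covers nivolumab monotherapy in bladder cancer. Its single administration row is labelled "Nivolumab (240 mg or 480 mg", and it carries a mark in every study-week column from 0 to 12: weeks 0, 2, 4, 6, 8, 10 and 12. The next cell of the same row, beyond week 12, reads "q 2 wks (240 mg) OR q 4 wks (480 mg". Footnote a, attached to this row, says "Nivolumab may be dosed no less than 11 days from the previous dose of drug" and does not distinguish the two doses. Footnote j says that assessments "should follow the frequency of Nivolumab treatment (q 2 weeks or q 4 weeks", but it is attached only to cells beyond week 12.

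Section 9.0 states that treatment "will follow the treatment plan described in section 4.2". Section 4.2 in turn refers the reader to the Section 10 flowcharts for the scheduling of study events. Neither section says which prevails if they differ.

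**The concern.** Within one row, the two options are separated after week 12 and merged before it. For 240 mg the marks agree with Section 4.2. For 480 mg, the marks at weeks 2, 6 and 10 have no counterpart in a 4-weekly schedule, and nothing on the page says that they do not apply.

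Two things are at stake. The first is exposure: taken at face value, the grid allows the larger dose at the shorter interval during weeks 0-12, and footnote a does not rule that out. The second is the assessment of compliance. Section 16.1.1 has monitors check sites against the protocol, and Section 16.3.2 counts any non-adherence as a deviation. A 480 mg patient can satisfy Section 4.2 and fall short of the flowchart, or satisfy the flowchart and depart from Section 4.2. Dose-intensity and deviation summaries then depend on which page is used.

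**Working it through.** **Inputs.** Visit marks, the 3-day visit window and the 11-day minimum come from Flowchart 1 (Section 10.1). Doses and intervals come from Sections 4.2 and 5.0.

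**1. The 11-day figure.** A 14-day interval less the 3-day window is 14 - 3 = 11 days, which reproduces footnote a. That it was derived this way is an inference, because the documents give no derivation. The same arithmetic on 28 days is 28 - 3 = 25 days. This second figure only shows that the footnote fits one of the two intervals; it is not offered as a rule. A gap of 11 days between 480 mg doses would satisfy footnote a but not a 4-weekly schedule.

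**2. Visits.** Marked visits, weeks 0-12: 7. Visits on a 4-weekly schedule: weeks 0, 4, 8 and 12, so 4. The difference is 7 - 4 = 3 (weeks 2, 6 and 10).

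**3. Cumulative dose** = dose x number of administrations.

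| Reading | Weeks 0-10 | Weeks 0-12 |
|---|---|---|
| 240 mg every 2 weeks (Section 4.2) | 6 x 240 = 1,440 mg | 7 x 240 = 1,680 mg |
| 480 mg every 4 weeks (Section 4.2) | 3 x 480 = 1,440 mg | 4 x 480 = 1,920 mg |
| 480 mg at every marked visit (literal Flowchart 1) | 6 x 480 = 2,880 mg | 7 x 480 = 3,360 mg |

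Weeks 0-10 are the fairer comparison, because the two Section 4.2 schedules deliver the same total there. The literal reading is 2,880 / 1,440 = 2 times that total. Including week 12, it is 3,360 / 1,680 = 2 times the 240 mg schedule and 3,360 / 1,920 = 1.75 times the 480 mg schedule.

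**4. The other flowcharts.** In Flowchart 2 the 240/480 mg row has no 2-weekly marks and pairs each dose with its interval, so there is no conflict of visits; only the undivided footnote a is shared. In Flowchart 3 the 11-day sentence belongs to a footnote on the 1 mg/kg row, not the 240/480 mg row, so the point does not extend to it.

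**The case against.** The strongest reply is that the protocol already settles the matter. Section 9.0 sends treatment to Section 4.2 and uses the Section 10 schedules for assessments and research procedures. Dose and interval are paired in Sections 1, 4.2 and 5, and again in the Flowchart 1 row beyond week 12. No sentence anywhere prescribes 480 mg every 2 weeks, and a careful investigator would probably follow Section 4.2. Much of this stands, and it limits the weight of the point. It does not remove the conflict: Section 4.2 points back to the flowcharts for scheduling, there is no rule of precedence, and the weeks 0-12 grid has no cross-reference.

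Several stronger readings are tempting but not supported:

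- **That footnote a contradicts the 4-weekly schedule.** It is a minimum gap, and a minimum below 28 days is compatible with dosing every 28 days. It only fails to exclude a shorter gap. The visit marks are the real evidence.
- **That the crossover condition of at least four monotherapy doses is distorted by the flowchart.** The fourth dose falls at week 6 on the 2-weekly schedule and at week 12 on the 4-weekly one because Section 4.2 itself allows both intervals. Correcting the flowchart would not change that, and Section 4.2 also permits earlier crossover after discussion with the principal investigator.
- **That harm is shown.** Section 3.0 describes a phase 1 study with doses up to 10 mg/kg every 2 weeks that reached no maximum tolerated dose. At the 80 kg planning weight in Section 5.0, 480 mg is 480 / 80 = 6 mg/kg. This does not make any schedule right, but the documents do not demonstrate the harm.
- **That sites work from the flowchart alone.** The documents do not say so. Section 5.0 refers to a pharmacy manual in Appendix 1, which is not reproduced and cannot be checked.

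**Conclusion.** The conflict is real but confined to the 480 mg option in weeks 0-12 of Flowchart 1. The 240 mg option is consistent throughout, and the row is consistent with Section 4.2 beyond week 12. Its size on a literal reading is a doubling of cumulative dose over weeks 0-10, or three apparently missed doses for a 480 mg patient treated per Section 4.2. The doubling assumes that a site gave 480 mg at every marked visit despite Sections 4.2 and 5; nothing in the documents indicates that any site did.

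This is an internal inconsistency in an operative dosing table, worth correcting because it is cheap to correct. It is not evidence of a flawed design. Under Post-Treatment Follow-up, Section 4.2 says that from Amendment 21 patients in active follow-up leave the study ahead of closure. That lowers the prospective risk, although whether anyone is still receiving treatment is not stated. Past dosing must still be judged against one unambiguous schedule.

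**What to change.** Reconcile the weeks 0-12 administration row of Flowchart 1 with Section 4.2, showing separately for each dose option which visits carry a dose. Reconcile footnote a in the same way where it applies to the 240/480 mg rows of Flowcharts 1 and 2, so that the minimum interval is stated for each option. Which dose, visits or interval should stand is for the sponsor and investigators to decide.

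Exposure and deviation summaries should also state the schedule against which each patient's dosing in weeks 0-12 was judged.

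The cost is a table and footnote correction by amendment, with the IRB steps in Section 16.3.1. It needs no new procedures and no change to sample size or analysis.

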7. All toxicities attributed to prior anti-cancer therapy other than alopecia and fatigue must have resolved to grade 1 (CTCAE version 4) or baseline before administration of study drug. Subjects with toxicities attributed to prior anti-cancer therapy and which are not

expected to resolve and result in long lasting sequelae such as neuropathy after platinum-based therapy, are permitted to enroll.

8. Positive test for hepatitis B virus (HBV) using HBV surface antigen (HBV sAg) test or positive test for hepatitis C virus (HCV) using HCV ribonucleic acid (RNA) or HCV antibody test indicating acute or chronic infection.
9. Known history of testing positive for human immunodeficiency virus (HIV) or known acquired immunodeficiency syndrome (AIDS).
10. History of allergy to study drug component or history of severe hypersensitivity reaction to any monoclonal antibody
11. Women who are breast feeding or pregnant as evidenced by positive serum pregnancy test (minimum sensitivity 25 IU/L or equivalent units of HCG) done within 14 days of first dosing and urine test within 72 hours of first dosing.
12. Women of childbearing potential (WOCBP) not using a medically acceptable means of contraception throughout the study treatment and for at least 23 weeks following the last dose of study treatment (5 half-lives of study drug plus 30 days duration of ovulatory cycle).

WOCBP are defined as those who has experienced menarche and who has not undergone successful surgical sterilization (hysterectomy, bilateral tubal ligation, or bilateral oophorectomy) or is not postmenopausal. Post-menopausal is defined as:

- Amenorrhea ≥ 12 consecutive months without another cause, or*
- For women with irregular menstrual periods and on hormone replacement therapy (HRT), a documented serum follicle stimulating hormone (FSH) level > 35 mIU/mL*

13. Male subjects who are unwilling to use contraception during the treatment and for at least 31 weeks after the last dose of study treatment (5 half-lives of study drug plus 90 days duration of sperm turnover).
14. Subjects who are compulsorily detained for treatment of either a psychiatric or physical (e.g., infectious disease) illness.

Restricted Concomitant Treatments

1. Immunosuppressive agents (except to treat a study-drug related adverse event)
2. Systemic corticosteroids > 10 mg daily prednisone equivalent (except to treat a study-drug related adverse event or as per section 4.2)

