Disease Staging	X								
Disease Assessment by RECIST 1.1 (including MRI or CT brain at screening)	X			Every 6 weeks (+/- 7 days) from first dose for the first 24 weeks and then every 12 weeks (+/- 7 days) thereafter until study discontinuation. ⁱ MRI or CT brain required at screening, but only necessary for subsequent disease assessments in patients with known disease metastatic to the CNS ^f					
Tumor Biopsy	X			2 weeks (-/+5 days) from first dose and before 2 nd dose of therapy ^g				At tumor progression (+ 14 days) ^g	
Other Examinations									
Eligibility Assessment	X								
Demographics	X								
Medical History	X								
ECOG, Vital Signs (including Height, Weight), Physical Exam & collection of concomitant medications	X		X	X	X	X	q 2 weeks / q 4 weeks ^j	X	X
EKG	X								
Adverse Events Assessment	X		X	X	X	X	q 2 weeks / q 4 weeks ^j	X	X
Labs & Assays									
Pregnancy Test (see Section 5.2.17, serum based.) ^b		3 mL						X	X
Urine pregnancy test (within 3 days prior to dosing) ^b			X	X	X	X	q 2 weeks / q 4 weeks ^j		
Chemistry (Comprehensive Metabolic Panel, LDH, TSH) ^c		X	X	X	X	X	q 2 weeks / q 4 weeks ^j	X	X
Blood Hematology (CBC with differential) ^c		X	X	X	X	X	q 2 weeks / q 4 weeks ^j	X	X
Research Blood Draw [mL] ^c	60mL		60mL	60mL	60mL	60mL		60mL	
HIV, Hepatitis B and Hepatitis C tests	X								
Survival Follow-up ^d								X	

- a. Nivolumab may be dosed no less than 11 days from the previous dose of drug.
- b. Pregnancy tests are not required if the patient is male or a woman of child-bearing potential.
- c. Blood drawn prior to dosing drug. Blood must be drawn at all required timepoints. Results of thyroid functions tests are not required prior to dosing drug.
- d. Patients will be followed up by telephone (or office visit) every 12 weeks (+/- 2 weeks) for 4 years from the start of treatment or until death. Follow-up calls or visits should begin 12 weeks +/- 2 weeks from the last study contact.
- e. *First dose of nivolumab monotherapy is on week 12 (+/- 3 days)*

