- f. Patients who discontinue treatment due to toxicity will continue to follow the study procedures (without treatment) for 12 weeks from the start date. They will require all disease assessments according to study protocol, however, after 12 weeks, all other study assessments (PE, Laboratory assays) will be performed every 12 weeks (+/-7 days). If patients discontinue treatment due to toxicity after they have been on treatment for 12 weeks, then the q 12 week follow up will begin after the patient's end of treatment. If the patient did not have an end of treatment visit, the q 12 week follow up will begin after the patient's last dose. Patients who experience progression of disease after discontinuing treatment early due to toxicity should move to survival follow-up. Patients in toxicity follow-up who initiate treatment with a new therapy will be immediately moved to survival follow-up.
- g. Optional
- h. Patients with a proven ability to tolerate treatment who have been on study for longer than one year will have visits with physicians every 4 weeks and treatment-only visits in between.
- i. Patients who have completed 26 weeks of treatment may elect to complete disease assessment scans every 6 months (24 weeks). This will continue until study discontinuation, under the treating investigator's discretion
- j. Frequency of ECOG, Vital Signs, Physical Exam, AE Assessments and all lab panels should follow the frequency of Nivolumab treatment (q 2 weeks or q 4 weeks) and should occur simultaneously within the same visit

Flowchart 3 - Nivolumab plus Ipilimumab Combination Treatment for Patients with Bladder Cancer Eligible for Crossover (or Reinduction with Combination Treatment for Bladder or Melanoma Patients)

Study Section	Baseline ^a	Initial Treatment				Treatment beyond Week 12 (up to 2 yrs) ^{f, i} (+/- 3 d)	End of Treatment	
		0	3 (+/- 3 d)	6 (+/- 3 d)	9 (+/- 3 d)		Last day	Last day +6 weeks (+/- 1 wk)
Study Week		0	3 (+/- 3 d)	6 (+/- 3 d)	9 (+/- 3 d)			
Study Day	-28 to 0	1	22	43	64			
Drug Administration								
Nivolumab 1 mg/kg ^b		X	X	X	X			
Ipilimumab 3 mg/kg		X	X	X	X	Re-induction (if applicable)		
Nivolumab 240 mg or 480 mg						q 2 wks (240 mg) OR q 4 wks (480 mg)		
Tumor Assessments								

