Disease Assessment by RECIST 1.1 (MRI or CT brain only necessary in patients with known disease metastatic to the CNS)	X	Every 6 weeks (+/- 7 days) from first dose for the first 24 weeks and then every 12 weeks (+/- 7 days) thereafter until study discontinuation MRI or CT brain only necessary in patients with known disease metastatic to the CNS ^{g, j}						
Tumor Biopsy	X ^h	2 weeks (- 5, +5 days) from first dose and before 2 nd dose of therapy ^h				At tumor progression (+ 14 days) ^h		
Other Examinations								
Eligibility Assessment	X							
Demographics	X							
Medical History	X							
ECOG, Vital Signs (Height, Weight), Physical Exam & collection of concomitant medications	X	X	X	X	X	q 2 weeks / q 4 weeks ^k	X	X
EKG	X							
Adverse Events Assessment	X	X	X	X	X	q 2 weeks / q 4 weeks ^k	X	X
Labs & Assays								
Pregnancy Test (see Section 5.2.17, serum based.) ^c	3 mL						X	X
Urine pregnancy test (within 3 days prior to dosing) ^c		X	X	X	X	q 2 weeks / q 4 weeks ^k		
Chemistry (Comprehensive Metabolic Panel, LDH, TSH) ^d	X	X	X	X	X	q 2 weeks / q 4 weeks ^k	X	X
Blood Hematology (CBC with differential) ^d	X	X	X	X	X	q 2 weeks / q 4 weeks ^k	X	X
Research Blood Draw [mL] ^d	60mL	60mL	60mL	60mL	60mL		60mL	
HIV, Hepatitis B and Hepatitis C tests								
Survival Follow-up ^e							X	

- a. Baseline procedures do not need to be repeated for reinduction combination treatment for bladder or melanoma patients.
- b. For patients with melanoma, ipilimumab will be dosed at 3 mg/kg and nivolumab at 1 mg/kg, for patients with bladder cancer ipilimumab will be dosed at 3 mg/kg and nivolumab at 1 mg/kg. Nivolumab may be dosed no less than 11 days from the previous dose of drug.
- c. Pregnancy tests are not required if the patient is male or a woman not of child-bearing potential
- d. Blood drawn prior to dosing drug. Blood must be drawn at all required timepoints. Results of thyroid functions tests are not required prior to dosing drug.
- e. Patients will be followed up by telephone (or office visit) every 12 weeks (+/- 2 weeks) for 4 years from the start of treatment or until death. Follow-up calls or visits should begin 12 weeks +/- 2 weeks from the last study contact.
- f. *First dose of nivolumab monotherapy is on week 12 (+/- 3 days)*

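### Flowchart 2 (melanoma combination), footnote b, omits "not" and so exempts women of child-bearing potential from pregnancy testing, against Flowcharts 1 and 3 and Section 9.0

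*Combined protocol and SAP*

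**What the plan says.** Flowchart 2 in Section 10.1 schedules two pregnancy tests for melanoma patients. The serum test falls at baseline, on the last day of treatment and 6 weeks after that. The urine test falls at weeks 0, 3, 6 and 9 and then follows the maintenance dosing interval. Both rows carry footnote b: "Pregnancy tests are not required if the patient is male or a woman of child-bearing potential".

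The same section states the rule twice more. Flowchart 1 (bladder monotherapy), footnote b: "Pregnancy tests are not required if the patient is a male or a woman not of child-bearing potential". Flowchart 3, footnote c: "Pregnancy tests are not required if the patient is male or a woman not of child-bearing potential". The title of Flowchart 3 extends it to "Reinduction with Combination Treatment for Bladder or Melanoma Patients", so it covers a melanoma patient only if she is re-induced.

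Section 9.0 covers both regimens ("Treatment of protocol eligible patients with nivolumab or nivolumab and ipilimumab will follow the treatment plan described in section 4.2") and lists: "Pregnancy test (serum or urine)- only if WOCBP". It describes the items on that list as "considered routine and will be performed according to the schedules in section 10.0 with indicated time windows".

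Section 6.2, exclusion 11, rules out pregnancy by a serum test and a urine test, "done within 14 days of first dosing and urine test within 72 hours of first dosing".

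**The concern.** A visit flowchart is what site staff work from. Here the footnote reverses a safety rule in the operative schedule for one cohort, so anyone applying it as written would leave out the tests in exactly the women who need them.

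What is at stake is detection of a pregnancy during or shortly after combination checkpoint blockade. Exclusion 12 requires contraception, which lowers the chance of a pregnancy but does not detect one. Section 17.2.1 requires pregnancies to be reported to the drug supplier, which presupposes that they are found. The protocol should not give two opposite answers on who is tested.

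**Working it through.** No formula applies: the point depends on no rate, effect size or sample-size calculation. The check is a comparison of text.

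**1. The four statements side by side.**

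| Place | Applies to | Consequence for women of child-bearing potential |
|---|---|---|
| Section 10.1, Flowchart 1, footnote b | Bladder, nivolumab alone | Tested |
| Section 10.1, Flowchart 2, footnote b | Melanoma, combination | Exempt |
| Section 10.1, Flowchart 3, footnote c | Bladder crossover; re-induction in either cohort | Tested |
| Section 9.0, list of routine interventions | Both regimens | Tested |

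Three agree and Flowchart 2 stands alone.

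**2. Is it a deliberate difference?** No. Taken literally, footnote b exempts men and women who can become pregnant, leaving only women who cannot. Two scheduled test rows would then serve no purpose. Adding one word makes the footnote match Flowchart 3 exactly and agree with Section 9.0.

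**3. Could it be an artefact of the text extraction?** That is unlikely. The sentence is complete and grammatical, with no gap or redaction mark. It is current schedule text, not a description of superseded text.

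**4. Which tests does it touch?** Exclusion 11 secures the serum test and the urine test before the first dose for both cohorts, whatever the footnote says. That leaves the urine tests at weeks 3, 6 and 9, the urine tests with maintenance dosing, and the serum tests on the last day and 6 weeks later.

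**5. Does another place time those later tests correctly for melanoma?** Section 9.0 names the right population but sends the reader to Section 10.0 for timing, which for this cohort is Flowchart 2. Flowchart 3 carries the right rule but reaches melanoma patients only at re-induction. The appendices were not among the text examined.

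**6. How many patients?** Section 14.0 plans 10 melanoma patients. The number who are women of child-bearing potential is not given, so the range is 0 to 10.

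**7. Any effect on the analysis?** None. Section 4.1 has the melanoma cohort analysed descriptively, and no pregnancy-test result enters an endpoint.

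**The case against.** The strongest reply is that the protocol already resolves the slip. The literal reading defeats itself, Section 9.0 states who is tested, exclusion 11 covers the start of treatment, and exclusion 12 requires contraception during treatment and for at least 23 weeks afterwards. Most of this stands: the intent is not in doubt and the remaining risk is small. It does not make the schedule correct, because Flowchart 2 is still the table that times the later tests for this cohort and its footnote still says the reverse.

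Three stronger readings are tempting, and the documents do not support them.

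- *A reader might infer that women entered the study, or were treated, without pregnancy testing.* Exclusion 11 requires tests before the first dose, and nothing in the documents shows that any later test was missed.
- *A reader might infer that a site could skip the later tests and still be compliant.* Section 9.0 would be breached, and a monitor who compares records with the whole protocol under Section 16.1.1 could see that.
- *A reader might count the tests at risk per patient.* No firm count is available. Footnote f of Flowchart 2 keeps patients who stop for toxicity on study procedures without saying whether pregnancy tests continue, and Section 4.2 allows treatment beyond two years, so there is no fixed upper limit.

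A dedicated retrospective check of the melanoma records is not warranted either. No missed test is shown, and Sections 16.1 and 16.1.1 already provide compliance audits at least twice a year and monitoring visits every 4 to 8 weeks with source review.

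**Conclusion.** The footnote is wrong as written and should be corrected. It is a drafting error in an operative safety instruction, confined to one flowchart and to the tests after the first dose, for between 0 and 10 women. It has no bearing on power, estimation or any endpoint.

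The conclusion rests on the text alone and assumes only that Flowchart 2 is the schedule sites use for melanoma patients outside re-induction. Prospective benefit is limited: Section 4.2 says that, as of Amendment 21, patients on active follow-up are to come off study in preparation for closure.

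**What to change.** Replace footnote b of Flowchart 2 with the wording already used in Flowchart 3: "Pregnancy tests are not required if the patient is male or a woman not of child-bearing potential". This adds one word and no procedures, and an administrative amendment or a clarification letter would carry it.

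As a purely clerical matter, the same edit can repair the serum-test row of all three flowcharts. Those rows point to Section 5.2.17, which does not exist in the current numbering. Section 8.0 cites Section 6.2 for the same test, and that is the reference to use. This does not change who is tested or when, and it adds nothing to the weight of the point.
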